Thus, the significance of the study lies in its investigation of the combined therapeutic effects of CKC and weight-shifting exercises as a potential strategy for enhancing postural stability and overall functional outcomes in patients with unilateral post-mastectomy lymphedema. By addressing the challenges of postural instability and balance deficits, this study aims to contribute to the development of more effective rehabilitation interventions, ultimately improving the quality of life for affected individuals.

Delimitations:

This study will be delimited in the following aspects:

1. Subjects:

Sixty female patients with unilateral post mastectomy lymphedema will be randomly divided into four equal groups in number, each one has 15 patients.

2. Equipment and tools:

2.1. Measurement equipment:

2.1.a. Kinesis Balance™ fall prevention app: smartphone-based machine learning algorithm for assessing standing balance (**Greene et al., 2021**).

2.1.b. Time up and go (TUG) test: for assessing dynamic balance and gait efficiency (**Tomar et al., 2024**).

2.1.c. Functional reach test: for assessing Functional reach and dynamic balance (**Alahmari et al., 2021**).

2.2. Therapeutic equipment and tools:

2.2.a. Closed kinetic chain exercises.

2.2.b. Weight shifting exercises.

Hypothesis:

It will be hypothesized that:

Closed kinetic chain and Weight shifting exercises have no significant effect on postural stability in unilateral post mastectomy lymphedema.

Basic Assumptions:

It will be assumed that:

- All patients will continue in the study.
- All patients will follow the instructions during the treatment.
- All patients will be informed about and understood the details of the research procedure.
- All patients enrolled in the study will have their informed consent.
- The clinical methods of measurement will be reliable and valid.

Definitions of terms:

The following terms are defined for the clear understanding of the terminology that will be used in the present study:

1. Closed kinetic chain exercises (CKC):

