Sample size calculation was done using Anteroposterior stability index, as reported in (Elsayeh et al, 2018), with 95% power at $\alpha = 0.05$ level, number of measurements 2, for 4 groups and effect size = 0.6 using F-test MANOVA repeated measures within and between interaction. The minimum proper sample size is 52 subjects, adding 8 subjects (15%) as drop out, so total sample size is 60 subjects, 15 subjects in each group. The sample size was calculated using G*Power software (version 3.0.10) (figure 1).

[figure not shown]

Figure (1): sample size calculation

Sixty patients who have unilateral post mastectomy lymphedema will participate in this study. Their ages will range from 40 to 60 years. The patients will be subdivided randomly into four equal groups by using simple randomization technique 1:1 ratio to four equal groups according to sample size calculation (15 patients for each group). The allocation will be performed with a blinded investigator using sealed opaque envelopes including a code for each group to avoid allocation bias. They will be selected from the Outpatient Clinic of Faculty of Physical Therapy, Cairo University and Alexandria oncology center.

All participants were informed about nature and the effect of measurement and treatment methods and have signed the informed consent which includes their agreement to participate in the study (**Appendix I**). They were instructed to report any side effects during management.

1.1- Design of the study:

The study will be four-armed, single-blind (assessor), parallel-group, randomized control trial.

1.1.a- Group A (n= 15) (CKC group):

This group will include 15 patients who will receive closed kinetic chain exercises, in addition to complex decongestive therapy (CDT) for the treatment of lymphedema. CDT includes (skin care, manual lymphatic drainage, compression bandages, compression garments and exercises). The total exercise time will be 30 minutes, three times per week for eight weeks.

1.1.b- Group B (n= 15) (WS group):

This group will include 15 patients who will receive weight shifting exercises, in addition to complex decongestive therapy (CDT) for the treatment of lymphedema. The total exercise time will be 30 minutes, three times per week for eight weeks.

1.1.c- Group C (n= 15) (Combined group):

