This group will include 15 patients who will receive closed kinetic chain and Weight shifting exercises, in addition to complex decongestive therapy (CDT) for the treatment of lymphedema. The total exercise time will be 60 minutes; 30 minutes of

CKC and 30 minutes of WS exercise three times per week for eight weeks.

1.1.d- Group D (n= 15) (control group):

This group will include 15 patients who will receive complex decongestive therapy (CDT) for the treatment of lymphedema. CDT includes (skin care, manual lymphatic drainage, compression bandages, compression garments and exercises).

1.2 Criteria for the patient selection:

1.2. a. Inclusion Criteria:

- Women who had a history of BCRS with upper limb lymphedema.
- Age range of 40-60 years.
- The body mass index (BMI) is less than 30 Kg/m².
- Consciousness and ability to communicate orally or in writing.
- Treatment by unilateral mastectomy with lymph node dissection.
- No obvious abnormal spine morphology or postural abnormalities visible to the naked eye.
- All participants had moderate lymphedema according to the lymphedema severity assessment.

1.2.b. Exclusion Criteria:

The potential patients will be excluded if they meet one of the following criteria:

- Patients with metastases.
- Differences between lower limb length.
- Having acute or chronic vestibular, neurological, and orthopedic diseases.
- Surgery related to spine causing limitation of motion.
- Women with psychiatric disorders, reconstructive surgery.
- Bilateral mastectomy.

- Diagnosis with a neurological, skeletal, or rheumatic disorder or other disease that seriously affects body posture.
- History of bodily injury such as a spinal, shoulder, or neck injury, resulting in permanent alteration of the normal body posture prior to the unilateral mastectomy.
- Failure to complete follow-up for any reason over the course of the study.
- Peripheral polyneuropathy, cognitive dysfunction.
- Patients taking medication that affects body balance.
- Severe arthritis or orthopedic conditions in their lower extremity
- Poor conditioning, acute pain in any reason,
- Neurological disorders including visual problems.

2-Equipment:

2.1- Measurement equipment:

2.1.a. Kinesis Balance™ fall prevention app:

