Smartphone-based machine learning algorithms for assessing standing balance. The app uses a questionnaire on clinical falls risk factors, combined with a standing balance test and machine learning algorithms to assess balance and fall risk. A reference data set is embedded within the app and was used to compare against the smartphone inertial sensor data. The algorithm includes data quality checks to ensure tests are performed correctly including checking phone is oriented correctly during the test, removing signal artefact resulting from movements due to changes in initial positioning of the phone as well as detection and removal of unusual behavior or phone movement during the test (**Greene et al., 2021**).

Smartphone data were sampled at the maximum rate allowed by the operating system. To ensure data were sampled evenly, data were interpolated to a 100 Hz

sampling rate using linear interpolation. Accelerometer and gyroscope data from the inertial sensor were band-pass filtered between 0.1–5 Hz and calibrated to produce acceleration and angular velocity vectors (**Cerca., 2018**).

Built-in sensors in every smartphone, including accelerometers and gyroscopes, are key to making smartphones capable of detecting balance. Therefore, by combining mobility and built-in IMUs, smartphones offer the potential to provide an objective and convenient balance assessment method. Furthermore, smartphones have been applied to individuals who have experienced stroke and have been proven feasible in assessing balance (**Hou et al., 2019**).

Test-retest reliability and effect sizes for stability measures obtained with a force plate and smartphone as well as correlations between force plate and smartphone measures based on a large sample of older adults. The test-retest reliability of the smartphone outcome parameters was moderate (0.5– 0.75) to good (0.75– 0.9). smartphone application is a valid and reliable way to measure balance (**De Groote et al., 2021**).

The results of this study show some of the highest correlation between a mobile device application and that of the results measured from long-accepted force plate. A similar study had a correlation of 0.63 with regards to positional sway. Therefore, the approach to the smartphone application presented here allows for an accurate way to capture the positional balance and sway without need of the stationary force plate (**Cimera and Voloshin., 2021**).

2.1.b. Time up and go test (TUG):

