Lateral weight-shifting, in particular, is essential for maintaining posture under dynamic conditions and is commonly performed in various activities of daily living (**Inoue et al., 2021**).

3-Procedures of the study:

3.1-Measurement procedures:

All patients will be evaluated before and after eight weeks of using closed kinetic chain and weight shifting exercises.

3.1.a. Kinesis Balance™ fall prevention app:

Patients will be instructed to hold the phone firmly against their sternum and stand with their eyes open, in a semi-tandem stance, for 30 s. The app contains audio and visual instructions on how to prepare for and complete the test as well as an audio cue to indicate test start and stop.

[figure not shown]

Figure (2): Shows Smartphone app for assessment of balance and falls risk using questionnaire and standing balance test (in semi-tandem stance **adapted** from (Greene et al., 2021).

3.1.b. Time Up and Go Test (TUG):

Patients will be asked to stand up from a chair with armrests, walk three meters, turn, walk back, and sit down, figure (3). The time taken to complete this task will be measured in seconds using a stopwatch (Tomar et al., 2024).

[figure not shown]

Figure (3): Shows Principle of the timed-up-and-go (TUG) test **adapted** from (Nierat et al., 2016).

3.1.c- Functional Reach Test (FRT):

The patient will enter a standing position on a line marked on the floor. An inch tape will be attached to a wall at approximately shoulder height of the subject. The therapist will stand 5–10 feet away from the patient and instruct them to stand close to the wall without touching it, while facing the inch tape, with the shoulder flexed at 90° and the hand in a fist, figure (4). The therapist will record the starting position at the knuckle of the third metacarpal head on the ruler. The patient will then be instructed to reach as far forward as possible along the length of the tape without moving their feet. The therapist will once again record the location of the knuckle of the third metacarpal. Patients will be required not to lean against the wall during the test. If they lose balance, the therapist will stop the test. The scores will be determined by assessing the difference between the starting and ending positions. Three trials will be conducted with one minute of rest between each trial, and the average distance will be recorded in centimeters (**Alahmari et al., 2021**).

[figure not shown]

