- **Step-up and step-down**

Patients will perform forward, backward and lateral step-ups and step-downs using a 5cm – high sturdy wooden box. They will be instructed to keep their trunk upright. Patients will perform 10 repetitions of each component of the exercise.

[figure not shown]

Figure (5): Shows closed kinetic exercises adapted from (Ng et al., 2022).

3.2.b- Weight shifting exercises (WS):

The training will be conducted on both a stable surface and an unstable surface (balance board) and will consist of the following five tasks, figure (6):

1. In a standing position, shift the weight left and right maximally.
2. In a standing position, shift the weight forward and backward maximally.
3. In a standing position, perform bending and stretching of both knees.
4. In a standing position, raise and lower both feet's heels.
5. While sitting on a chair, perform sit-to-stand exercises on the balance board.

Each session will last for 30 minutes, occurring three days a week for a duration of 8 weeks (Lee et al., 2015).

Figure (6): Shows Weight Shifting adapted from (Diebal et al., 2011)

3.3. Complex decongestive therapy:

Complex decongestive therapy (CDT) for the treatment of lymphedema for both groups. CDT includes (skin care, manual lymphatic drainage, compression bandage and exercises).

4-Statistical procedures:

The collected data will be statistically analyzed using:

- Descriptive statistics (mean and standard deviations).
- Inferential statistics; ANOVA will be used to compare between subjects characteristics of the three groups.
- Shapiro-Wilk test will be used for testing normality of data distribution.
- Mixed MANOVA will be used to compare parametric measured variables between and within groups.
- Statistical analysis will be conducted using SPSS for Windows, version 20 (SPSS, Inc., Chicago, IL). Statistical significance will be set at the ($p < 0.05$).

REFERENCES

2. Ahmed, Y. F., Shafeek, M. M., & El-Kasem, S. T. A. (2021). Effect of cold versus heat modalities on dynamic balance in healthy adolescents. *Physiotherapy Quarterly*, 29(2), 56-61.

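### The mixed MANOVA treats baseline as a time level and so compares change scores; ANCOVA of week 8 on baseline would be more precise for each outcome

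*Protocol*

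**What the plan says.** Chapter III, section 4 (Statistical procedures) names one efficacy model: "Mixed MANOVA will be used to compare parametric measured variables between and within groups". The ANOVA in the same list is for subject characteristics only. No baseline covariate is named anywhere in the protocol.

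Section 3.1 (Measurement procedures) sets two assessments: "All patients will be evaluated before and after eight weeks of using closed kinetic chain and weight shifting exercises". The sample size calculation uses "number of measurements 2, for 4 groups and effect size = 0.6 using F-test MANOVA repeated measures within and between interaction", with 95% power at α = 0.05, and arrives at 52 patients, raised to 60 (15 per arm).

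There are three outcome measures (Delimitations, section 2.1): the Kinesis balance app, the Timed Up and Go test ("Time up and go (TUG) test: for assessing dynamic balance and gait efficiency") and the functional reach test ("Functional reach test: for assessing Functional reach and dynamic balance").

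Complex decongestive therapy (CDT) is common to all four arms. For the control arm the protocol says: "This group will include 15 patients who will receive complex decongestive therapy (CDT) for the treatment of lymphedema". The three exercise arms receive it as well.

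**The concern.** With two time points and baseline as one of them, each outcome's group-by-time test is a one-way comparison of change scores. A change score subtracts the whole baseline value, whereas the best prediction of week 8 subtracts only the fraction ρ of it (equal SDs). The over-subtraction adds noise. With 15 patients per arm and simple randomisation, chance baseline differences are likely and between-arm estimates will be imprecise. The baseline data that could narrow them are collected anyway.

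A secondary point concerns which term carries the conclusion. The sample size section powers the interaction, but the analysis section speaks of comparisons both between and within groups. The protocol does not say it will conclude from any term other than the interaction. If it did, two terms would mislead. The between-groups main effect averages baseline with week 8 and so halves a treatment effect. A within-group pre-post change cannot separate exercise from CDT.

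**Working it through.** **Inputs from the protocol.** Four groups, two measurements, f = 0.6, α = 0.05, 52 evaluable patients (13 per arm), 60 enrolled (15 per arm).

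**Assumed input.** The baseline to week-8 correlation ρ is not given, so 0.5, 0.75 and 0.9 are used. Section 2.1.a says "The test-retest reliability of the smartphone outcome parameters was moderate" (0.5 to 0.75) to good (0.75 to 0.9). This covers the same range but is not an eight-week correlation. SDs are taken as equal at both times.

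**Step 1: reproduce the plan's figure.** Noncentral F with df 3 and N − 4, and λ = N f². At N = 52, λ = 52 × 0.36 = 18.72 and power is 0.951. At N = 51 power is 0.946. The stated 52 is reproduced, which confirms that the powered test is the interaction with baseline as a time level.

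**Step 2: the interaction is a change-score test.** On a simulated four-arm data set the interaction F and the one-way ANOVA F on change scores were both 0.9182.

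**Step 3: variance ratio.** In units of the outcome variance, a change score has residual variance 2(1−ρ) and ANCOVA has 1−ρ². The excess is 2(1−ρ) − (1−ρ²) = (1−ρ)². The ratio is (1−ρ²)/[2(1−ρ)] = (1+ρ)/2.

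**Step 4: power for one outcome at N = 52.** The ANCOVA effect size is 0.6/√((1+ρ)/2), with df 3 and 47.

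| ρ | Variance ratio | f, ANCOVA | Power, formula | Power, simulated with chance imbalance |
|---|---|---|---|---|
| 0.5 | 0.75 | 0.693 | 98.8% | 98.6% |
| 0.75 | 0.875 | 0.641 | 97.3% | 97.1% |
| 0.9 | 0.95 | 0.616 | 96.0% | 95.6% to 95.8% |

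The planned test has 95.1% by formula and 95.0% to 95.1% in simulation (40,000 runs).

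**Step 5: interval half-width for a difference between two arms, 15 per arm, in outcome SD.** Change score: t √(2(1−ρ)) √(2/15). ANCOVA: t √(1−ρ²) √(2/15).

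| ρ | Formula, change to ANCOVA | Simulated with chance imbalance | Narrower (simulated) |
|---|---|---|---|
| 0.5 | 0.731 to 0.634 | 0.728 to 0.637 | 12.6% |
| 0.75 | 0.517 to 0.484 | 0.515 to 0.486 | 5.6% |
| 0.9 | 0.327 to 0.319 | 0.326 to 0.320 | 1.6% |

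By formula the narrowing is about 13%, 6% and 2.5%. Allowing for the estimated slope by a factor of about 1 + 1/(N−6), the precision gain disappears only above ρ of about 0.96.

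**Step 6: does the gain carry over to a joint test?** Simulated power of the mixed MANOVA against a MANCOVA with three baselines (4,000 runs, Pillai, assumed between-outcome correlation 0.5, one arm differing equally on all outcomes):

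| ρ | f = 0.6, 13 per arm | f = 0.4, 15 per arm |
|---|---|---|
| 0.5 | 93.8% v 97.7% | 66.6% v 77.8% |
| 0.75 | 93.8% v 95.3% | 66.2% v 69.6% |
| 0.9 | 93.7% v 92.8% | 65.6% v 65.6% |

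The per-outcome figures therefore do not transfer to the joint test.

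**Step 7: the other two terms.** Main effect: the mean of 0 at baseline and d at week 8 is d/2. Within-arm test, for illustration only: with no exercise effect, an assumed CDT gain of 0.3 to 0.5 SD, ρ = 0.75 and n = 15, a paired t-test is significant 33% to 72% of the time.

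**The case against.** The strongest reply is that nothing here is an error. The measurement schedule, the sample size calculation and the model agree with each other, and the test is valid and adequately powered. The benefit depends on an unknown ρ and is slight if ρ is high. If all 60 patients complete, the planned test has 97.6% power, against 98.0% to 99.5% for ANCOVA over the assumed range (slope allowance included), so the power gain is small. Nor does adjustment cure the imprecision of 15 per arm. For the joint test that the protocol actually names, baseline adjustment brings no reliable gain. Splitting that test into three also raises a multiplicity question that the joint test avoids.

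Most of this stands and sets the limits of the point: it concerns efficiency, and the joint interaction needs no change. It does not remove the point. The protocol itself chose the model, so this is not a detail left to a later document. Readers will want the differences between arms outcome by outcome, and those can be estimated more precisely from data already collected. The multiplicity cost comes from testing three outcomes separately and not from ANCOVA: at 0.05/3, change scores would have 88.1% power, below ANCOVA at each assumed ρ. The remarks on the main effect and the within-group tests are conditional on how results are read, and the conclusion does not rest on them.

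**Conclusion.** The concern holds, as a loss of precision and not a bias. For each outcome, the planned test has a variance larger than ANCOVA's by the factor 2/(1+ρ): 1.33, 1.14 and 1.05 at ρ of 0.5, 0.75 and 0.9, before the small cost of estimating the slope. The sample size of 52 is correct for the planned test and is unaffected.

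The algebra is secure. Its practical size is less so, because it rests on an assumed ρ and on equal SDs at both times. The change is worth making because it is nearly free, although the trial would remain valid without it.

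**What to change.** In section 4, state that the four randomised groups will be compared on each outcome's week-8 value by ANCOVA with that outcome's own baseline as covariate. Report adjusted between-group differences with 95% confidence intervals and base conclusions on them. Say how the three outcomes share the 5% error rate: one named primary outcome, or Holm. Treat within-group pre-post tests as descriptive, and draw no conclusion from the between-groups main effect. If a single joint test is wanted, keep the planned group-by-time interaction for that purpose.

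**Cost.** Protocol wording only, with no extra patients, visits or data. Each ANCOVA uses one error degree of freedom, already included in the figures. Three separate tests without adjustment could take the family-wise error to 1 − 0.95³ = 14.3% if the outcomes were independent. At 0.05/3 each, simulated per-outcome power at 52 patients and f = 0.6 is 95.8%, 92.0% and 89.2% at ρ of 0.5, 0.75 and 0.9. Naming one primary outcome removes that cost.
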